4 STUDY ENDPOINTS

4.1 Primary Endpoint

The primary endpoint of the study is the change from baseline to Week 8 in mean systolic blood pressure (SBP) as measured by 24-hr ABPM.

4.2 Secondary Endpoints

The secondary endpoints of the study are:

- Change from baseline to Week 8 in mean diastolic blood pressure (DBP) as measured by 24-hr ABPM;
- Mean change in SBP and DBP from baseline to Week 8 as measured in clinic.

4.3 Exploratory Endpoints

The exploratory endpoints of the study are:

- Mean hourly changes in SBP and DBP from baseline to Week 8, defined as the mean change from baseline at each hour;
- Change in mean daytime and nighttime SBP as measured by 24-hr ABPM from baseline to Week 8;

- Change from baseline to Week 8 in nighttime “dipping” of SBP, and the percentage of subjects with a normal SBP “dipping” pattern at Week 8. A normal “dipping” pattern of SBP will be defined as a reduction of mean nighttime SBP of $\geq 10\%$ relative to mean daytime SBP during the same 24-hr recording;
 - SBP dipping is calculated as: $100 \times [(\text{mean daytime SBP} - \text{mean nighttime SBP}) / \text{mean daytime SBP}]$
- Change from baseline to Week 8 in nighttime “dipping” of DBP, and the percentage of subjects with a normal DBP “dipping” pattern at Week 8. A normal “dipping” pattern of DBP will be defined as a reduction of mean nighttime DBP of $\geq 10\%$ relative to mean daytime SBP during the same 24-hr recording;
 - DBP dipping is calculated as: $100 \times [(\text{mean daytime DBP} - \text{mean nighttime DBP}) / \text{mean daytime DBP}]$
- Percentage of subjects meeting the following BP thresholds at baseline and Week 8 as measured by 24-hr ABPM;
 - SBP: ≥ 160 mmHg for 2 consecutive readings; ≥ 180 mmHg for 2 consecutive readings;
 - DBP: ≥ 100 mmHg for 2 consecutive readings; ≥ 110 mmHg for 2 consecutive readings;
- Percentage of subjects with the average of three successive BP meeting the following thresholds at baseline and each post-baseline visit as measured in clinic;
 - SBP: ≥ 160 mmHg; ≥ 180 mmHg; ≥ 20 mmHg increase from baseline;
 - DBP: ≥ 100 mmHg; ≥ 110 mmHg; ≥ 15 mmHg increase from baseline;
- Change from baseline to Week 8 in mean 24-hr heart rate, mean daytime heart rate, mean nighttime heart rate, and mean hourly heart rate;
- Percentage of subjects meeting the following heart rate thresholds at baseline and Week 8 as measured by 24-hr ABPM;
 - > 100 bpm for 2 consecutive readings; > 100 bpm for at least 1 hour; > 100 bpm for at least 2 hours; > 100 bpm for at least 3 hours; > 100 bpm for at least 4 hours; mean daytime heart rate > 100 bpm;
- Percentage of subjects meeting the following heart rate thresholds at baseline and each post-baseline visit as measured in clinic;
 - > 100 bpm;
 - ≥ 10 bpm increase from baseline; ≥ 20 bpm increase from baseline
 - ≥ 80 bpm at baseline and ≥ 10 bpm increase from baseline; ≥ 90 bpm at baseline and ≥ 10 bpm increase from baseline; ≥ 100 bpm at baseline and ≥ 10 bpm increase from baseline;
- Mean percent change in body weight from baseline to Week 8.

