Exploratory Endpoints:	
The exploratory endpoints of the study are:
 
• Mean hourly change in SBP and DBP from baseline to Week 8;• Change in mean daytime and nighttime SBP as measured by 24-hr ABPM from baseline to Week 8;• Change from baseline to Week 8 in nighttime “dipping” of SBP, and the percentage of subjects with a normal SBP “dipping” pattern at Week 8. A normal “dipping” pattern of SBP will be defined as a reduction of mean nighttime SBP of $\geq 10\%$ relative to mean daytime SBP during the same 24-hr recording;
○ SBP dipping is calculated as: $100 \times [(\text{mean daytime SBP} - \text{mean nighttime SBP}) / \text{mean daytime SBP}]$• Change from baseline to Week 8 in nighttime “dipping” of DBP, and the percentage of subjects with a normal DBP “dipping” pattern at Week 8. A normal “dipping” pattern of DBP will be defined as a reduction of mean nighttime DBP of $\geq 10\%$ relative to mean daytime DBP during the same 24-hr recording.
○ DBP dipping is calculated as: $100 \times [(\text{mean daytime DBP} - \text{mean nighttime DBP}) / \text{mean daytime DBP}]$ 
For assessment of daytime and nighttime blood pressure, “night” will be defined as the mean of all systolic and diastolic blood pressure values recorded between 24:00 and 05:00 (inclusive) and “day” will be defined as the mean of all systolic and diastolic blood pressure values recorded between 07:30 and 21:30 (inclusive);
 
• Change from baseline to Week 8 in mean 24-hr heart rate, mean daytime heart rate, mean nighttime heart rate, and mean hourly heart rate;• Mean percent change in body weight from baseline to Week 8.
Safety Evaluation:	Safety will be evaluated by analyses of adverse events, changes in laboratory parameters, changes in ECG, physical exam findings, vital signs, and requirement for rescue therapy for blood pressure and T2DM.

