8.2 Exclusion Criteria

To be eligible for enrollment into this study, subjects must not meet any of the following criteria at screening (unless otherwise specified):

1. Screening blood pressure of $> 140/90 \text{ mmHg}$;

2. Known allergy or hypersensitivity to phentermine or topiramate, any prior use of a combination of phentermine and topiramate for weight loss or use of phentermine or topiramate for any indication within the past 3 months;
3. Weight gain or loss of greater than 5 kg, use of a very low-calorie diet, or participation in a formal weight loss program (investigational or otherwise) within the past 3 months (this includes: Weight Watchers and related dietary/lifestyle intervention programs; prepared food programs; prescribed or over-the-counter weight loss medications; dietary supplement or herbal preparations, teas, or tinctures intended for weight loss; or any medically-supervised fast or very low calorie diet);
4. Obesity of a known genetic or endocrine origin;
5. Previous bariatric surgery or other non-surgical weight loss procedure;
6. History of any eating disorders (e.g., bulimia, binge eating disorder) within the past year;
7. History or presence of a seizure disorder;
8. History of drug or alcohol abuse within the past year or positive drug test;
9. Smoking cessation within the past 3 months or intent to quit during the study;
10. Use of antihypertensive medications, antidiabetic medications, statins or other lipid lowering agents, or CPAP therapy that has not been stable for at least 3 months prior to randomization;
11. Chronic conditions/diseases associated with a reduced ability to maintain autonomic regulation such as multiple sclerosis or any known autonomic neuropathy;
12. History of glaucoma, increased intraocular pressure, or any past or present use of medications to treat increased intraocular pressure;
13. Clinical evidence of hyperthyroidism, or use of thyroid hormone treatment that has not been stable for at least 3 months prior to randomization;
14. Use of chronic systemic glucocorticoid therapy, or any other steroid hormone therapy that has not been stable for at least 3 months at the time of randomization;

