13.0 STATISTICAL CONSIDERATIONS

13.1 Statistical Analysis and Methods

All analyses will be performed on the intent-to-treat (ITT) population (all randomized subjects who received at least one dose of study drug). Analyses of a per-protocol population may also be utilized to confirm the presence or absence of a pressor signal. Subject demographic data and baseline characteristics will be summarized for all subjects enrolled in the study.

Detailed methodology for summary and statistical analyses of the data collected in this clinical trial will be documented in a prospectively developed Statistical Analysis Plan (SAP). This document may modify the plans outlined in the protocol; however, any major modifications of the primary endpoint definition and/or its analysis will also be reflected in a protocol amendment. Additional statistical analyses other than those described in this section may be performed if deemed appropriate and included in the plan.

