13.1.5 Analysis of Exploratory Endpoints

Exploratory endpoints that are continuous measurements will be analyzed using the same methods as described above for the primary endpoint. For categorical outcomes, differences between treatments will be evaluated using a non-parametric method. Details will be provided in the SAP.

The exploratory endpoints will be the difference between treatment groups (top-dose VI-0521 vs. placebo, top-dose VI-0521 vs. phentermine, and phentermine vs. placebo) in the change from baseline in:

- Mean hourly changes in SBP and DBP from baseline to Week 8, defined as the mean change from baseline at each hour.
- Change in mean daytime and nighttime SBP as measured by 24-hr ABPM from baseline to Week 8;
- Change from baseline to Week 8 in nighttime “dipping” of SBP, and the percentage of subjects with a normal SBP “dipping” pattern at Week 8. A normal “dipping” pattern of SBP will be defined as a nighttime reduction of mean nighttime SBP of $\geq 10\%$ relative to mean daytime SBP during the same 24-hr recording.
 - SBP dipping is calculated as: $100 \times [(mean\ daytime\ SBP - mean\ nighttime\ SBP) / mean\ daytime\ SBP]$.
- Change from baseline to Week 8 in nighttime “dipping” of DBP, and the percentage of subjects with a normal DBP “dipping” pattern at Week 8. A normal “dipping” pattern of DBP will be defined as a nighttime reduction of mean nighttime DBP of $\geq 10\%$ relative to mean daytime SBP during the same 24-hr recording.
 - DBP dipping is calculated as: $100 \times [(mean\ daytime\ DBP - mean\ nighttime\ DBP) / mean\ daytime\ DBP]$.
- Change from baseline to Week 8 in mean 24-hr heart rate, mean daytime heart rate, mean nighttime heart rate, and mean hourly heart rate;
- Mean percent change in body weight from baseline to Week 8.

For assessment of daytime and nighttime blood pressure, “night” will be defined as the mean of all systolic and diastolic blood pressure values recorded between 24:00 and 05:00 (inclusive) and “day” will be defined as the mean of all systolic and diastolic blood pressure values recorded between 07:30 and 21:30 (inclusive).

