7.2.3 Analysis of Exploratory Endpoints

Analysis of exploratory endpoints will be performed on the PP population using the observed case data.

All change from baseline exploratory endpoints will be analyzed using ANCOVA models in a similar manner to the primary and secondary endpoints. For the endpoints on percentage of subjects with a normal SBP and DBP ‘dipping pattern’ at Week 8, a Cochran-Mantel-Haenszel (CMH) χ^2 test that is stratified by sex, age and hypertensive status will be used for analysis. Corresponding estimates of the common Mantel-Haenszel relative risk will be provided along with 95% confidence intervals (CIs). For the endpoints on percentage of subjects meeting the BP or heart rate thresholds, descriptive summary will be provided.

Example SAS codes for CMH test are:

No sensitivity analysis is planned for the exploratory endpoints.

In addition, all 24-hr ABPM measurements including blood pressure and heart rate that are summarized in the endpoints will be presented in a listing.

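### The cut-off for a normal diastolic dip is set against daytime systolic pressure in SAP 4.3 and Protocol 7.3 and 13.1.5, contradicting the printed formula and the synopsis

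*SAP*

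**What the plan says.** A normal DBP dip is defined in four places.

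- **SAP 4.3:** "reduction of mean nighttime DBP of $\geq 10\%$ relative to mean daytime SBP during the same 24-hr recording". The formula under the same bullet has daytime DBP minus nighttime DBP in the numerator and daytime DBP in the denominator.
- **Protocol 7.3:** the same sentence, with the same DBP-only formula beneath it.
- **Protocol 13.1.5:** "nighttime reduction of mean nighttime DBP of $\geq 10\%$ relative to mean daytime SBP during the same 24-hr recording", again followed by the DBP-only formula.
- **Protocol synopsis (2.0):** "reduction of mean nighttime DBP of $\geq 10\%$ relative to mean daytime DBP during the same 24-hr recording", with the same formula. Here sentence and formula agree.

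SAP 7.1.4 fixes the day and night clock windows but not the reference pressure. SAP 7.2.3 says how the percentage of normal dippers is compared: a Cochran-Mantel-Haenszel "test that is stratified by sex, age and hypertensive status will be used for analysis", with a Mantel-Haenszel relative risk and 95% confidence interval. It does not restate the definition.

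**The concern.** The formula defines a continuous quantity, DBP dipping in percent. The 10% threshold that turns it into a yes/no outcome appears only in the sentence, and in the SAP that sentence names the wrong pressure. The correct version exists only in the protocol synopsis. A programmer who codes the responder flag from the SAP sentence would therefore pass a wrong variable to the CMH test and the relative risk.

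The sentence also has two literal readings, which err in opposite directions:

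- **Reading A:** night DBP must lie at least 10% below day SBP. Almost every subject meets this, so the endpoint carries almost no information and the relative risk is forced towards 1.
- **Reading B:** the fall in DBP must be at least 10% of day SBP. SBP exceeds DBP, so this is always stricter than 10% of day DBP and fewer subjects qualify.

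If the choice between sentence and formula were left until treatment codes are known, it would become an avoidable post hoc decision.

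**Working it through.** **Inputs.** The 10% cut-off and the two candidate reference pressures come from the sections listed above. The documents give no ambulatory pressures and no distribution of dipping, so every pressure and distribution below is an assumption. The pair 140/90 is borrowed from the clinic screening limit in Protocol 8.2. There is no figure in the plan to reproduce.

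**Conditions for a normal dip**

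- Formula: DBP fall ≥ 0.10 × day DBP.
- Reading A: night DBP ≤ 0.90 × day SBP.
- Reading B: DBP fall ≥ 0.10 × day SBP, which as a percentage of day DBP is 10 × (day SBP / day DBP).

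| Day BP (mmHg) | Formula: fall of at least | Reading A: night DBP at most | Reading B: fall of at least | Reading B as % of day DBP |
|---|---|---|---|---|
| 120/75 | 7.5 | 108 | 12 | 16.0 |
| 125/70 | 7 | 112.5 | 12.5 | 17.9 |
| 130/80 | 8 | 117 | 13 | 16.25 |
| 135/85 | 8.5 | 121.5 | 13.5 | 15.9 |
| 140/90 | 9 | 126 | 14 | 15.6 |

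Reading B depends only on the ratio of SBP to DBP. Other assumed pairs give 15.0% (120/80), 15.3% (130/85), 16.4% (115/70), 17.3% (130/75) and 17.5% (140/80). All the pairs tried therefore fall between 15.0% and 17.9%. More extreme pulse pressures go beyond that range: 140/70 gives 20%.

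**What this does to individual subjects**

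- Under reading A, a subject with no DBP dip at all scores 100 × (130 − 80)/130 = 38.5% at 130/80, and 36% to 44% across the five pairs in the table. To fail at 130/80, night DBP must exceed 117, a rise of more than 37/80 = 46% over day DBP.
- Under reading B, a subject with a true 12% DBP dip scores 100 × (0.12 × 80)/130 = 7.4% at 130/80, and 6.7% to 7.7% across the five pairs. That subject is counted as a non-dipper.

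**What this could do to the percentage of normal dippers.** Take every subject at 130/80 and let the true DBP dip be normally distributed. The share of normal dippers is 1 − Φ((c − mean)/SD), with c = 10 for the formula and c = 16.25 for reading B.

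| Assumed mean, SD of dip (%) | Formula | Reading B | Difference (points) |
|---|---|---|---|
| 8, 6 | 36.9% | 8.5% | 28.4 |
| 8, 8 | 40.1% | 15.1% | 25.0 |
| 10, 6 | 50.0% | 14.9% | 35.1 |
| 10, 8 | 50.0% | 21.7% | 28.3 |
| 12, 6 | 63.1% | 23.9% | 39.2 |
| 12, 8 | 59.9% | 29.8% | 30.1 |
| 14, 6 | 74.8% | 35.4% | 39.4 |
| 14, 8 | 69.1% | 38.9% | 30.2 |

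Reading A gives about 100% in every row.

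**The case against.** The strongest reply is that this is a copying slip from the SBP bullet just above, and that the correct formula on the next line makes the intention plain. A programmer will already have derived DBP dipping for the continuous endpoint and would naturally apply the 10% cut-off to that variable. Reading A would expose itself in the first table, because nearly everyone would be a dipper, so only reading B could pass unnoticed. The percentages above rest on assumed pressures and an assumed distribution. They show prevalence under two cut-offs, not the effect on a between-arm comparison. SAP 7.2.3 is an analysis section and need not repeat a definition. SAP section 1 also allows justified deviations that are documented in the study report.

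Most of this stands. The intended reference can be recovered, the harm requires someone to follow the sentence over the formula, and the illustration does not quantify bias in the relative risk. The silence of SAP 7.2.3 is not a separate defect; it only means that nothing later in the SAP settles the matter. What does not follow is that the text can be left alone. The threshold is stated only in the faulty sentence, the same fault stands in three current sections of two documents, and the planned output is an inferential test with a confidence interval. A pre-specified responder definition should not have to be inferred.

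**Conclusion.** The concern holds. SAP 4.3 and Protocol 7.3 and 13.1.5 contradict their own formula and the synopsis on the reference pressure for a normal DBP dip. The formula shows that the intended comparison is DBP with DBP.

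Followed literally, the sentence either makes nearly all subjects normal dippers or raises the effective cut-off from 10% to roughly 15–18% of daytime DBP for the pressures tried. In the assumed scenarios the second reading moves 25–39% of all subjects from dipper to non-dipper. Those percentages are illustrative only.

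The consequence is limited to the Week 8 percentage of normal DBP dippers, an exploratory outcome outside the testing hierarchy. The change in DBP dipping as a continuous measure has a consistent formula everywhere. The primary and secondary endpoints, the sample size and the type I error control are not involved.

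**What to change.** In the DBP sentence of SAP 4.3, replace daytime SBP with daytime DBP, so that a normal DBP dip is a value of at least 10% from the printed formula. Do this before unblinding. The documents do not give the current blinding status; if codes are already open, record the correction and its reason in the study report, as SAP section 1 provides.

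The cost is one word. No new analysis, data or programming is needed beyond applying the existing dipping variable. Protocol 13.1 says of the SAP: "This document may modify the plans outlined in the protocol". It asks for a protocol amendment only for major changes to the primary endpoint or its analysis, so the SAP correction is enough to govern this analysis. Protocol 7.3 and 13.1.5 should be aligned with the synopsis when the protocol is next amended; a separate amendment is not warranted.

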4.4 Safety Endpoints

The safety endpoints include evaluation of the following:

- Adverse events (AEs)
- Changes in laboratory parameters
- Changes in Electrocardiograms (ECG)
- Physical exam findings
- Vital signs
- Requirement for rescue therapy for blood pressure and type 2 diabetes mellitus (T2DM)

5 ANALYSIS POPULATIONS

The following analysis populations will be defined for study summaries and analyses.

5.1 Enrolled Population

Enrolled Population will be comprised of all enrolled subjects (non-screen failures), regardless of randomization. The Enrolled Population will be used for by-subject listings when appropriate.

5.2 Intent-to-Treat (ITT) Population

ITT Population will be comprised of all randomized subjects who received at least one dose of study drug. Subjects will be analyzed according to the treatment group they are allocated to by randomization, regardless of early dropout or being exposed to wrong study medication. The ITT population will be used for summaries of subject disposition, demographic and baseline subject characteristics, medical history, concomitant medication, protocol deviations and efficacy evaluations.

5.3 Safety Population

Safety Population will be comprised of all randomized subjects who received at least one dose of study drug. Subjects will be analyzed according to the treatment received. The Safety Population will be used for safety evaluations.

5.4 Per Protocol (PP) Population

PP Population will be comprised of ITT subjects who met all of the following criteria:

- Compliant to study treatment (defined as $\geq 80\%$ treatment compliance as specified in [Section 6.5](#));
- Last daily dose of study drug administered on the same date that ABPM was initiated at Visit 4A (first day of Week 8/End of Study or Early Termination);
- Had at least 23.5 hours of ABPM data (i.e. blood pressure and heart rate data) at baseline and at Week 8/End of Study or Early Termination, and at least 75% of 24-hr ABPM readings (or equivalently 48 readings during the 24-hr period) are not missing;
- Subjects with any major protocol deviation that had impact on ABPM readings will be excluded from the PP Population.

The PP population will be used to assess the primary and secondary endpoints as primary analyses. Subject inclusion in the PP population will be determined and documented prior to database lock and treatment unblinding.

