11.3 Vital Signs

Vital signs (systolic blood pressure, diastolic blood pressure, heart rate, respiration rate, temperature) will be assessed at Screening, Randomization, Week 4, and Week 8/end of study or early termination. Subjects should be seated comfortably for at least 10 minutes prior to assessing vital signs. Heart rate and respiratory rate measurements should be made by counting events (heartbeats or breaths) for a period of 30 seconds and multiplying these values by 2 to obtain the rates per minute. A calibrated blood pressure monitor should be employed for blood pressure measurements. The same cuff should be used for the same subject across multiple visits when blood pressure is performed. The same person should perform all assessments for a given subject.

Clinic blood pressure for determining hypertension should be the average of three successive BP readings, collected at least 2 minutes apart. The mean of the three values will be recorded as the subject's blood pressure.

11.4 24-hr Ambulatory Blood Pressure Monitoring (24-hr ABPM)

At Baseline and at Week 8/end of study or early termination, 24-hr ABPM will be performed non-invasively using a validated oscillometric monitor provided by a central vendor. Blood pressure and heart rate will be measured every 20 minutes from 6:00 to 22:00 hours, and every 30 minutes from 22:01 to 5:59 hours for 24 consecutive hours, while subjects continue normal routine activities. The monitor will be attached in the morning and removed after at least 24 hours. Data will be uploaded to a computer at the end of the recording session and prior to discharging the subject from the study visit, site staff will review the data to assure that: (1) at least 80% of the readings are valid, (2) there are at least 24 hours of data, and (3) there are no more than two consecutive hours of missing data. If any of these criteria are not satisfied, subjects will be asked to repeat the assessment for an additional 24 hours. ABPM hook up will be done by qualified staff.

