7.1.4 Handling of Ambulatory Blood Pressure Monitoring Data

For the 24-hr ABPM, blood pressure and heart rate will be measured every 20 minutes from 6:00 to 22:00 hours, and every 30 minutes from 22:01 to 5:59 hours for 24 consecutive hours. The baseline and post-baseline values for mean ABPM (SBP and DBP) will be calculated by taking the average of ABPM measurements over the given 24-hr time period.

For assessment of daytime and nighttime blood pressure, “night” will be defined as the mean of all systolic or diastolic blood pressure values recorded between 24:00 and 05:00 (inclusive) and “day” will be defined as the mean of all systolic or diastolic blood pressure values recorded between 07:30 and 21:30 (inclusive).

Mean hourly changes in blood pressure and heart rate will be calculated by taking the average of ABPM measurements available at each hour and calculating the change from baseline of the average. The measurements taken in the 60 minute duration prior to each hour will be used to get the average value. For example, the average of blood pressure measurements taken at 6:05, 6:25 and 6:45 will be defined as the mean blood pressure at 7:00.

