	Tributary	Within-treatment group comparison (effect at Week 8 minus the value at baseline): ✓ LSM for the within-group difference ✓ 95% CI of the LSM ✓ p-value

The following SAS programming codes will be applied:

```
PROC MIXED DATA=DATAIN;
  CLASS TREATMENT(REF='Placebo' [or 'Phentermine']) SEX AGE HYPSTATUS;
  MODEL CHG_SBP=TREATMENT SEX AGE HYPSTATUS BASE_SBP/SOLUTION DDFM=KR;
  LSMEANS TREATMENT/ALPHA=0.05 PDIFF CL;
```

RUN;

For subjects who discontinue from the study but complete Early Termination ABPM assessments, such measurements will be mapped to Week 8/End of Study or Early Termination for analysis. For subjects who have missing 24-hr SBP measurements at baseline or at Week 8 after mapping unscheduled visits, missing data will be imputed using the approach below. If the percentage of missing readings at either visit is $\leq 25\%$ (see [Section 5.4](#)), 24-hr mean SBP values will be calculated by taking the average of non-missing and imputed measurements over the 24-hr time period. Imputed measurements will be derived as follows:

1. For any intermediate missing observations between two non-missing readings BP_1 and BP_2 , missing observations will be imputed using the formula: $BP = (BP_2 - BP_1)/(t_2 - t_1) \times (t - t_1) + BP_1$; whereas t_1 , t , and t_2 are the time of the measurements respectively;
2. If missing observations are at the beginning or at the end, the beginning observations will be imputed as the average of non-missing and step 1 imputed data points from 6:00 to 22:00 hours. The end observations will be imputed similarly using data points from 22:01 to 5:59 hours.

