SHIFTPARAM2), the MI procedure outlined above will be executed. ANCOVA analysis will be run on all imputed datasets. Confidence intervals of the between-treatment comparisons estimated from the PROC MIANALYZE will be reported. The following shift parameters will be identified:

1. For non-inferiority: when the upper bound of the two-sided 95% confidence interval just crosses 3 mmHg;
2. For superiority: when the upper bound of the two-sided 95% confidence interval just crosses 0 mmHg.

Analysis of Missing Data Pattern

Number and percentage of subjects with at least 75% of non-missing 24-hr ABPM readings at baseline and Week 8 will be summarized by the following variables on the ITT Population:

- Baseline mean SBP as measured by 24-hr ABPM (< population median and \geq population median);
- Baseline mean DBP as measured by 24-hr ABPM (< population median and \geq population median);
- Sex (male and female);
- Age (< 50 and \geq 50 years);
- Race (white and not white);
- Hypertensive status (no medical diagnosis of or treatment for hypertension; medical diagnosis of hypertension treated with 0-2 antihypertensive agents; or medical diagnosis of hypertension treated with 3 or more antihypertensive agents).

Number and percentage of subjects with more than two consecutive hours of missing 24-hr ABPM readings will also be summarized by visit on the ITT Population.

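### The SAP drops the protocol's two-hour gap limit, so a Week 8 recording with most or all of its night missing can enter the primary analysis with a straight line in place of the night.

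*SAP*

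**What the plan says.** SAP 7.1.4 schedules readings "every 20 minutes from 6:00 to 22:00 hours, and every 30 minutes from 22:01 to 5:59 hours" and takes the 24-hr mean as the plain average of the readings.

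SAP 5.4 admits a subject to the per-protocol (PP) set if, at baseline and at Week 8, the subject "Had at least 23.5 hours of ABPM data" and "at least 75% of 24-hr ABPM readings (or equivalently 48 readings during the 24-hr period) are not missing". A further bullet excludes major protocol deviations that affected the ABPM readings. The PP set is the primary analysis population.

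SAP 7.2.1 fills gaps when no more than 25% of readings are missing. Its step 1 applies linear interpolation "For any intermediate missing observations between two non-missing readings", with no maximum gap length.

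Protocol 11.4 sets a stricter check at the site: at least 80% valid readings, at least 24 hours of data, and "there are no more than two consecutive hours of missing data". If a recording fails, the subject is asked to repeat it. Protocol 10.2 and 10.4 place this verification at baseline, before randomization, and again at Week 8.

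In the SAP the gap criterion survives only as a summary table in 7.2.1.1: "Number and percentage of subjects with more than two consecutive hours of missing 24-hr ABPM readings".

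**The concern.** The protocol's rule protects the night by limiting the gap. The SAP's rule counts readings and ignores where the missing ones fall. Readings are sparser at night, so the whole night is only a quarter of them, which is exactly the share the SAP allows to be missing. The monitor goes on in the morning, so the night is an interior gap and step 1 applies. A line from the last evening reading to the first morning reading misses most of the nocturnal fall, and the 24-hr mean comes out too high.

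The exposure is mainly at Week 8, because a verified baseline recording is required before randomization. An error at Week 8 alone passes undiluted into the change score.

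The other planned analyses do not correct it:
- The observed-case analysis (SAP 7.2.1.2) averages only the surviving, mostly daytime readings.
- The ITT multiple imputation (SAP 7.2.1.1) uses the same interpolation in its Step 1.
- The tipping-point analysis acts on Step 2, which covers only recordings with more than 25% missing.

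Night mean and dipping have no minimum number of night readings either.

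**Working it through.** **Reading counts (SAP 7.1.4).** Day: 16 h × 3 = 48. Night: 8 h × 2 = 16. Total 64, and 0.75 × 64 = 48, so the SAP's figure reproduces. Counting both 06:00 and 22:00 as day readings gives 49 + 15 = 64, and the floor is again 48.

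**Which recordings pass the 75% floor?**

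| Recording | Present | Share | SAP 75% | Protocol 80% | Protocol 2-hour limit |
|---|---|---|---|---|---|
| All day, no night | 48/64 | 75% | passes | fails | fails |
| Same, one day reading lost | 47/64 | 73.4% | fails | fails | fails |
| Off 23:00 to 6:00 (14 lost) | 50/64 | 78% | passes | fails | fails |
| Off midnight to 6:00 (12 lost) | 52/64 | 81% | passes | passes | fails |

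The last two rows matter most. They leave two and four readings to spare, and in the last row only the two-hour limit catches the gap.

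**Error in one recording.** Error = (missing readings / 64) × (mean of the line − true mean of the missing readings).

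Assumptions: daytime mean 130 mmHg, which is not in the documents, and a 10% dip (13 mmHg), which is only the plan's threshold for a normal pattern. Upper bound, with both ends of the line at daytime level and all 16 missing readings at full night level: 16/64 × 13 = 3.25 mmHg.

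Gradual transitions are more realistic, because 22:00 and 06:00 lie outside the SAP's day window (07:30 to 21:30) and its night window (24:00 to 05:00). Let SBP fall linearly from 21:30 to 24:00 and rise linearly from 05:00 to 07:30. Express each level as a fraction of the dip, on the 49 + 15 grid:
- **Whole night missing.** The ends of the line are at 0.2 (22:00) and 0.6 (06:00), so its mean is 0.40. The true mean of the 15 missing readings is 13.6/15 = 0.907. Error = 15/64 × 0.507 × 13 = 1.54 mmHg.
- **23:00 to 6:00.** The ends are at 0.4 and 0.6, mean 0.50. True mean 13.2/14 = 0.943. Error = 14/64 × 0.443 × 13 = 1.26 mmHg.
- **Midnight to 6:00.** The ends are at 0.8 and 0.6, mean 0.70. True mean 11.8/12 = 0.983. Error = 12/64 × 0.283 × 13 = 0.69 mmHg.

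On a 48 + 16 grid (night readings from 22:15, last day reading at 21:40) the whole-night error is 16/64 × (0.875 − 0.344) × 13 = 1.73 mmHg.

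The error is proportional to the dip. For a whole night missing at 130 mmHg:

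| Assumed dip | Gradual transitions | Both ends at daytime level |
|---|---|---|
| 5% | 0.8 to 0.9 mmHg | 1.6 mmHg |
| 10% | 1.5 to 1.7 mmHg | 3.25 mmHg |
| 15% | 2.3 to 2.6 mmHg | 4.9 mmHg |

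**Observed-case analysis, whole night missing, 10% dip.** The 49 day readings average 0.039 of the dip, so the error is 15/64 × (0.907 − 0.039) × 13 = 2.6 mmHg, larger than with interpolation.

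**Between arms.** The error is multiplied by the difference in the share of affected recordings. The documents give no such share. For an assumed 5-point difference the shift is 0.05 × 1.54 to 0.05 × 1.73, about 0.08 to 0.09 mmHg (0.16 at the upper bound). For 10 points it is 0.15 to 0.17 (0.33). For scale, the margin is 3 mmHg. With the planned SD of 10 mmHg and about 175 per arm after 5% dropout, the standard error of a difference is 10 × √(2/175) = 1.07 mmHg.

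**The case against.** The strongest reply is that such a recording should seldom reach the analysis. Week 8 has the same verify-and-repeat step as baseline, a night-free recording fails the site check, and SAP 7.1.5 uses the later assessment, so a good repeat replaces the faulty one. The PP definition can also remove the subject as a major deviation. This stands, and it limits the exposure to recordings whose repeat is refused or fails. It does not close the gap: subjects are only asked to repeat, and the deviation clause is a judgement with no stated gap limit.

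The night-free case at 48/64 tolerates no failed daytime reading (one on the 49 + 15 grid), and a monitor taken off for good at 22:00 after an 08:00 start leaves 43/64 = 67% and fails. That also stands. The 23:00 and midnight cases are less fragile. Nor must the cuff come off, since Protocol 11.4 itself warns of a kinked hose at night.

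A reader might infer that the 23.5-hour criterion can mean only the span of the recording. That does not follow: a quarter of the readings missing at scattered times is compatible with data in every hour. Span is the likelier reading, because the protocol lists hours of data and gap length as separate checks, but the SAP does not define the term.

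A reader might also infer unequal loss between arms, because Protocol 4.1 lists insomnia among the common adverse events. That sleepless subjects remove the cuff is not in the documents. Excess loss on VI-0521 would raise its apparent SBP and work against it; excess loss on a comparator would favour VI-0521.

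**Conclusion.** The point holds as a gap in the SAP's rules. As written, they allow a Week 8 recording without most or all of its night into the primary analysis, and following them gives a 24-hr mean that is too high. It is a route by which such recordings can enter, not evidence that they will be common.

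At an assumed 130 mmHg daytime mean and 10% dip, the error for a fully missing night is about 1.5 to 1.7 mmHg in that recording, with an upper bound of 3.25 mmHg. Shorter night gaps give less. A figure as high as 4.9 mmHg needs a 15% dip and both ends of the line at full daytime level; the documents support neither.

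These are errors in single recordings and should not be read against the 3 mmHg margin as if they were treatment differences. Loss that is balanced across arms largely cancels, and even an assumed 10-point imbalance shifts the difference by a few tenths of a mmHg at most. The case for acting is that the SAP relaxes the protocol's own quality limit for the primary endpoint without a stated reason, and that restoring it is cheap.

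**What to change.** Before database lock and unblinding, when PP membership is settled:

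1. In SAP 5.4, add the protocol's limit of two consecutive hours of missing data to the recording criterion, and say how a gap is measured.
2. In SAP 7.2.1 step 1, restrict interpolation to gaps of at most two hours.
3. Treat a recording with a longer gap like one with more than 25% missing: out of the PP set, and handled by Step 2 of the multiple imputation in the ITT analysis, so that the tipping-point analysis covers it too.
4. Apply the same criterion before computing night mean and dipping.
5. State whether the 23.5 hours means span or hours covered.

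The cost is SAP wording. The flag for gaps over two hours is already needed for the planned table. The downside is that a few subjects leave the PP set; they stay in the ITT analysis through multiple imputation.
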